5.3.6 Normalized AUC for COWS Total Score Post-SUBLOCADE Injection – Sensitivity Analysis

The normalized AUC analysis described in [Section 5.3.5](#) will be repeated, stratified by number of TM BUP doses during induction phase (1 dose, ≥ 2 doses) and during SUBLOCADE treatment phase (0 dose, ≥ 1 dose), and by enrollment before or after re-training ([Section 5.6](#)).

5.3.7 COWS Total Score Absolute Value and Change - Definition of Endpoint

The endpoints are the COWS total score at each scheduled assessment timepoint from the Pre-TM BUP timepoint for the last TM BUP dose during the induction phase through EOT (i.e., absolute value), and the change in COWS total score from the pre-TM BUP and pre-SUBLOCADE values at each timepoint.

5.3.8 COWS Total Score Absolute Value and Change - Main Analytical Approach

The absolute value and change in COWS total score will be summarized using descriptive statistics at each scheduled nominal timepoint. The summary for COWS values will start from the Day 1 Check-in timepoint for the last TM BUP dose in the induction phase through EOT. The summary for change in COWS total score from the Pre-TM BUP value or from the Pre-SUBLOCADE value will start from the first scheduled nominal timepoint post the last TM BUP dose in the induction phase or the SUBLOCADE injection through EOT.

The analysis will use observed data and will include subjects with the pre-TM BUP/pre-SUBLOCADE value and a COWS assessment at the scheduled timepoint of interest.

The mean COWS total scores (absolute value and change from pre-TM BUP and pre-SUBLOCADE) will be plotted over time for all scheduled timepoints.

5.3.9 COWS Total Score Absolute Value and Change – Supplemental Analysis

Individual subject plots of COWS absolute value over time will be produced, using the TM BUP analysis set and including all assessment timepoints (scheduled and unscheduled).

If the actual date/time for a scheduled COWS assessment is missing, the date/time will be imputed for the purpose of creating the AE and COWS listing (Section 5.5.2):

$\text{Date/Time}_{\text{current COWS}} = \text{actual date/time SUBLOCADE injection} + \text{nominal time}_{\text{current COWS}}$

5.3.10 OC-VAS Score Absolute Value and Change - Definition of endpoint

The OC-VAS score at each timepoint is the value marked on the paper source by the subject and recorded in the eCRF by site personnel.

The endpoints are the OC-VAS score at each scheduled assessment timepoint from Pre-TM BUP timepoint for the last TM BUP dose during the induction phase through EOT (i.e., absolute value), and the change in OC-VAS score from the pre-TM BUP and pre-SUBLOCADE values at each timepoint.

5.3.11 OC-VAS Score Absolute Value and Change - Main Analytical Approach

The absolute value and change in the OC-VAS score will be summarized using descriptive statistics. The summary for OC-VAS scores will start from the Day 1 Check-in timepoint for the last TM BUP dose in the induction phase through EOT. The summary for change in OC-VAS score from the Pre-TM BUP value or from the Pre-SUBLOCADE value will start from the first scheduled nominal timepoint post the last TM BUP dose in the induction phase or the SUBLOCADE injection through EOT.

The analysis will use observed data and will include subjects with at least one pre-TM BUP/pre-SUBLOCADE OC-VAS assessment and an OC-VAS assessment at the timepoint of interest.

The mean OC-VAS scores (absolute value and change from pre-TM BUP and pre-SUBLOCADE) will be plotted over time for all scheduled timepoints.

5.3.12 OC-VAS Score Absolute Value and Change – Supplemental Analysis

Individual subject plots of OC-VAS score absolute value over time will be produced, using the TM BUP analysis set and including all assessment timepoints (scheduled and unscheduled).

5.4 Exploratory Endpoint(s) Analysis

5.4.1 Precipitated Withdrawal from TM BUP – Definition of Endpoint

Precipitated withdrawal from a TM BUP induction dose will be defined as an increase in COWS by ≥ 6 from the Pre-TM BUP value for that TM BUP dose to the subsequent COWS assessment prior to the SUBLOCADE injection or the next TM BUP dose in the induction phase.

5.4.2 Precipitated Withdrawal from TM BUP – Main Analytical Approach

The frequency count, percentage and its 2-sided 95% exact confidence interval (CI) using binomial distribution Clopper-Pearson method (Clopper 1934) will be constructed for precipitated withdrawal from the first dose of TM BUP. The analysis will use observed data. A subject is considered eligible for the analysis if the subject has the Pre-TM BUP COWS assessment and a subsequent COWS assessment prior to the SUBLOCADE injection or the next TM BUP dose in the induction phase.

5.4.3 Peak and Overall Plasma Exposure to NMP – Definition of Endpoint

In addition to NMP plasma concentrations, the following PK parameters for NMP will be derived by non-compartmental analysis:

- C_{max} : maximum observed plasma concentration
- T_{max} : time of maximum observed plasma concentration
- AUC_{0-24hr} : area under the plasma concentration-time curve from time 0 to 24 hours post-SUBLOCADE dose.
- AUC_{last} : area under the plasma concentration-time curve from time 0 to the time of the last quantifiable concentration; calculated using the linear trapezoidal rule.
- AUC_{inf} : area under the plasma concentration-time curve from time 0 extrapolated to infinite time.

$$AUC_{inf} = AUC_{last} + \frac{C_{last}}{\lambda_z}$$

AUC_{inf} will be reported if the percent of extrapolation is less than 20% and if the coefficient of determination R_{sq} is at least 0.8. A minimum of three data points will be required. C_{last} is the last quantifiable plasma concentration, λ_z is the slope of the terminal phase in semi-logarithmic scale.

5.4.4 Peak and Overall Plasma Exposure to NMP – Main Analytical Approach

NMP plasma concentrations will be reported by the bioanalytical laboratory in units of ng/mL and converted to µg/mL ($\text{result}_{\mu\text{g/mL}} = \text{result}_{\text{ng/mL}} / 1000$) for analyses and listings.

NMP plasma concentrations will be summarized descriptively (number of observations, mean, SD, median, minimum, maximum, geometric mean and coefficient of variation) at each scheduled sampling time for the PK Analysis set.

Plasma concentration values reported as below the limit of quantitation (BLQ) will be treated as zero to calculate summary statistics of plasma concentration data.

Linear and semi-logarithmic plots of the mean NMP plasma concentration-time curves will be presented. Plots of individual plasma concentration-time curves will also be presented on linear and semilogarithmic scales with all subjects shown on a same figure. Individual time plots will present all concentrations measured for the subject using actual sampling times. Mean plots will present concentrations measured at the scheduled sampling times.

Individual plasma concentration data will be presented in the listings for all subjects.

For the calculation of PK parameters, actual sampling times, rather than scheduled sampling times, will be used. In addition, all plasma concentrations that are BLQ prior to the first measurable concentration will be set to zero. The BLQ values that are between measurable concentrations will be set to missing. If two or more consecutive BLQ concentrations are followed by quantifiable concentrations, these quantified values will be set to missing. If a BLQ concentration is followed by a quantifiable concentration, and the quantifiable concentration is then followed by two or more consecutive BLQ concentrations, the quantifiable concentration will be set to missing. The BLQ values following the last quantifiable time points will be set to missing. No concentration estimates will be imputed for missing sample values.

Summary statistics (number of observations, mean, SD, median, minimum, maximum, geometric mean and coefficient of variation) will be calculated for all relevant PK parameters. Individual PK parameters will be presented in the listings.

5.5 Analysis of Other Safety Assessments

The analysis of the Other Safety Assessments will utilize the safety analysis set, unless otherwise specified.

See [Section 6.5](#) for methods to handle missing safety data (e.g., partial dates).

5.5.1 Extent of Exposure

The extent of exposure will be summarized using the Enrolled Population. The number and percentage of subjects who received 1, 2, 3, etc. doses of TM BUP 4mg (i.e., the cumulative dose) during the induction and the SUBLOCADE treatment phases, and the number of subjects who received SUBLOCADE 300mg, will be summarized.

5.5.2 Adverse Events

A treatment emergent adverse event (TEAE) is defined as an AE observed after administration of the first TM BUP dose. The investigator determines the intensity of AEs and the relationship of AEs to study medication.

If a subject experiences an event both prior to the first dose of TM BUP and ongoing during the treatment, the event will be considered a TEAE (of the treatment) only if it has worsened in severity (i.e., it is reported with the date of worsening as the new start date/time) after starting administration of the TM BUP.

A TEAE summary table will present the number and percentage of subjects reporting a TEAE in the categories listed in Table 8.

Table 8 TEAE Summary Categories

Category
Subjects with Any TEAEs
With Study Medication-Related TEAEs
With Serious TEAEs (SAE)
With Study Medication-Related Serious TEAEs
With Severe TEAEs
With TEAE Leading to Death
With TEAE Leading to Study Medication Discontinuation
With TEAE Leading to Study Medication Interruption
With Serious TEAE Leading to Study Medication Discontinuation
With Serious TEAE Leading to Study Medication Interruption
With Adverse Events of Special Interest

The number and percentage of subjects reporting TEAEs during the treatment period will be presented by MedDRA system organ class (SOC) and preferred term (PT), each in descending order of frequency (then alphabetically in case of ties). The categories of TEAE listed above in Table 8 will be summarized in the same manner. TEAEs will also be summarized by intensity, system organ class and preferred term. The number of occurrences of TEAEs and study medication-related TEAEs will be summarized by PT. In addition, the number and percentage of fatal and fatal study medication-related treatment-emergent SAEs will be summarized separately by PT.

The summaries also will be presented for those AEs having a start date within 48 hours of the SUBLOCADE administration. These events will be defined as TEAEs where $0 \leq (\text{AE start date} - \text{SUBLOCADE injection date}) \leq 2$ days, and $0 \leq (\text{AE start date/time} - \text{SUBLOCADE injection date/time}) \leq 48$ hours.

In addition, the summaries of TEAEs, serious TEAEs, and related TEAEs will be presented for the TM BUP Analysis Set, separately for events with a start date/time during the Induction Phase and with a start date/time after the SUBLOCADE injection.

If more than one TEAE is coded to the same PT for the same subject, the subject will be counted only once for that PT using the most severe and most related occurrence for the summarizations by severity and by relationship to the study medication.

Listings will be presented for subjects with AEs, SAEs, AEs leading to discontinuation, and subjects who died (if any).

A chronological listing of COWS assessment dates/times and values, with AEs starting in each assessment interval, and administration dates/times of study medications will be produced.

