3.3 Other Safety Assessments

Major safety endpoints will include the proportion of subjects with TEAEs of the following types at any time during the treatment period (i.e., any time after administration of TM buprenorphine): TEAE, drug-related TEAE, serious TEAE, drug-related serious TEAE and TEAE leading to treatment discontinuation.

Additional safety endpoints will include assessment of laboratory results, vital signs and concomitant medications.

Withdrawal symptoms will be monitored by COWS (secondary endpoint), AEs, opioid craving (using OC-VAS; secondary endpoint) and sedation (using Sedation VAS).

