6.4 TM Buprenorphine Treatment and Early Termination

When an eligible subject's COWS is ≥ 8 and all pre-buprenorphine assessments have been completed, the subject will receive TM buprenorphine. Subjects experiencing precipitated withdrawal will be treated for withdrawal symptoms. If precipitated withdrawal occurs before SUBLOCADE administration, the TM induction may be restarted later on the same day at the discretion of the Investigator, based on the half-life of the opioid reported on the TLFB. Alternatively, the Investigator may permit the subject to return to the facility on another day (within the Screening Period). Returning subjects will repeat all Day 1 scheduled assessments.

A subject will be considered a TM Buprenorphine Early Termination if he/she is dosed with TM buprenorphine but is not dosed with SUBLOCADE. Reasons for early termination (e.g., withdrawal of consent, AE of precipitated withdrawal, allergic/hypersensitivity to buprenorphine) will be recorded in the eCRF. Subjects who discontinue from the study after TM buprenorphine administration and before SUBLOCADE administration, will be withdrawn from the study and contacted via

telephone 24 to 72 hours after TM buprenorphine administration to assess ongoing AEs and concomitant medications only.

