14.5 Analysis of Other Safety Assessments

Other safety assessments data will be analysed using the safety population, descriptive statistics for continuous endpoints (e.g., n, mean, median, SD, minimum and maximum), and frequency counts with percentages for discrete endpoints. Complete details of the safety analyses will be provided in the SAP.

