4 POPULATIONS FOR ANALYSIS

Data for all subjects will be assessed to determine if they meet the criteria for inclusion in each analysis population prior to releasing the database and classifications will be documented per standard operating procedures.

Table 6 Populations for Analysis

Population	Description
Screened	All subjects who sign the informed consent document.
Enrolled	A subject will be considered enrolled if he/she receives at least 1 dose of TM BUP.

Full Analysis Set	The FAS population consists of all subjects who receive a SUBLOCADE injection and have data for at least 1 COWS assessment at the Pre-SUBLOCADE timepoint just before the SUBLOCADE injection and a COWS assessment for at least one of the scheduled timepoints within 48 hours after SUBLOCADE injection. The FAS will serve as the primary population for the analysis of key endpoints in this study.
Safety Analysis Set	The safety population will be used for the safety analysis, and it consists of all subjects who received at least 1 dose of SUBLOCADE. The safety population will serve as the primary population for the analysis of safety assessments related to SUBLOCADE.
TM BUP Analysis Set	The TM BUP Analysis Set consists of all subjects who received at least 1 dose of TM BUP. This analysis set will be used for analysis of the exploratory safety endpoint related to TM BUP. (Note: this is the same population as Enrolled).
PK Analysis Set	The PK Analysis Set will be used for the Exploratory PK endpoint analysis and will consist of all subjects who received the SUBLOCADE injection and have at least one NMP plasma concentration measurement post-SUBLOCADE. Subjects in the PK population with protocol deviations or events that impact the quality of the PK data will be assessed on a case-by-case basis.

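### The discontinuation-TEAE endpoint opens at TM buprenorphine but is tabulated only in injected subjects, so AE stops before injection fall outside it

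*SAP*

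**What the plan says.** **Endpoint.** Protocol 3.3 names the major safety endpoints as proportions of subjects, ending with "drug-related serious TEAE and TEAE leading to treatment discontinuation". The window is "at any time during the treatment period (i.e., any time after administration of TM buprenorphine". SAP Table 2 repeats this. SAP 5.1.4 agrees: the overall treatment period joins the induction phase to the SUBLOCADE phase, and induction can end at the TM buprenorphine early-termination contact as well as at injection.

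**Analysis set.** Protocol 14.5 states: "Other safety assessments data will be analysed using the safety population". SAP 5.5 states: "The analysis of the Other Safety Assessments will utilize the safety analysis set, unless otherwise specified". SAP Table 6 defines that set: "it consists of all subjects who received at least 1 dose of SUBLOCADE".

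**Tables.** SAP Table 8 has the row "With TEAE Leading to Study Medication Discontinuation", and one for its serious counterpart. No other population is named for these rows, so the default applies. SAP 5.5.2 then says that "the summaries of TEAEs, serious TEAEs, and related TEAEs will be presented for the TM BUP Analysis Set", separately for events in the induction phase and after the injection.

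**Stops before injection are foreseen.** Protocol 6.4 defines the TM Buprenorphine Early Termination as a subject given TM buprenorphine but not SUBLOCADE, and adds: "Reasons for early termination (e.g., withdrawal of consent, AE of precipitated withdrawal, allergic/hypersensitivity to buprenorphine) will be recorded in the eCRF".

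**The concern.** Treatment in this study is TM buprenorphine followed by one injection. An AE can end treatment between the two: Protocol 4.1 discontinues a subject with a hypersensitivity reaction at that point, and Protocol 5.7 bars the injection after precipitated withdrawal or if there are clinical signs of sedation. A subject whose participation ends there falls inside the endpoint's time window but outside the population in which the endpoint is tabulated.

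The study objective is the safety and tolerability of starting SUBLOCADE after a single TM dose. The discontinuation endpoint is the item in Protocol 3.3 that most directly shows how often an AE breaks that sequence. Restricting it to injected subjects selects on having passed the step where such a break is foreseen. Read alone, the table could suggest that no TEAE led to discontinuation when some subjects had stopped during induction.

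**Working it through.** **1. Plan figures.** The documents state no expected discontinuation rate. Their only sample-size figures concern precipitated withdrawal with 15 subjects, and these reproduce: 1 − 0.90^15 = 0.794 and 1 − 0.95^15 = 0.537. The present point does not depend on them. Only the planned number injected, 15 (Protocol 14.2, SAP 3), is used below.

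**2. Who is counted where.**

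| Subject | In endpoint window (Protocol 3.3) | In Table 8 row (safety set) | In TM BUP set tables (SAP 5.5.2) |
|---|---|---|---|
| Injected, discontinues later for an AE | yes | yes | yes, but not identified as a discontinuation |
| AE after TM buprenorphine, re-induced, then injected | yes | yes, with induction TEAEs | yes |
| AE after TM buprenorphine, never injected | yes | **no** | yes, but not identified as a discontinuation |

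The third line is the gap.

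**3. Size, with assumed counts.** Let d be discontinuations for an AE after injection, k the subjects stopped by an AE before injection, and o the subjects leaving before injection for other reasons.

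- Safety set: d / 15. This does not depend on k.
- Endpoint as defined: (d + k) / (15 + k + o).

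With d = 0 and o = 0:

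| k | Safety set | Endpoint as defined | Exact 95% interval for the latter |
|---|---|---|---|
| 1 | 0/15 = 0% | 1/16 = 6.3% | 0.2 to 30.2% |
| 3 | 0/15 = 0% | 3/18 = 16.7% | 3.6 to 41.4% |
| 5 | 0/15 = 0% | 5/20 = 25.0% | 8.7 to 49.1% |

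The Clopper-Pearson intervals are added here to show precision. The SAP plans only a count and percentage for this row. For 0/15 the upper limit would be 1 − 0.025^(1/15) = 21.8%.

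**4. Sensitivity.** With one depot removal (d = 1), the safety set shows 1/15 = 6.7% for every k, against 2/16 = 12.5% at k = 1 and 4/18 = 22.2% at k = 3. With d = 0, k = 3 and two further non-AE exits (o = 2), the endpoint as defined is 3/20 = 15.0% against 0/15. In every case the safety-set figure does not respond to k.

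**The case against.** The strongest reply is that nothing is concealed, and much of it stands.

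- SAP 5.2 summarises reasons for discontinuing, by phase, in the Enrolled population, which is the same set as the TM BUP Analysis Set.
- AEs leading to discontinuation are listed (SAP 5.5.2), and listings default to the Screened population (SAP 5.1.5).
- Induction-phase TEAEs are tabulated in the TM BUP set.
- Precipitated withdrawal after the first TM dose has its own analysis with an exact interval (SAP 5.4.2) and is adjudicated in enrolled subjects (SAP 5.3.3.2).

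A reader might infer that pre-injection stops vanish from the report. The documents do not support that. But none of these outputs is the named endpoint. Disposition gives reasons without preferred terms, the TEAE summaries do not show which events stopped treatment, and the withdrawal analysis rests on a COWS threshold and does not cover hypersensitivity.

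A reader might also infer that the safety-set rate is zero by construction. That goes too far. Protocol 6.7.1 counts depot removal as discontinuing treatment, supplemental TM buprenorphine is possible after injection (Protocol 4.1), and precipitated withdrawal need not end treatment because induction may be restarted (Protocol 6.4). Low is a fair expectation; zero is not guaranteed.

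Nor is this an SAP departure from the protocol. Protocol 14.3.2 and 14.5 choose the same set, so the mismatch lies between endpoint definition and analysis set in both documents.

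Finally, the TM BUP sentence could be read as covering all of Table 8. That is strained: serious and related TEAEs are themselves Table 8 rows, yet they are named separately. The same omission should not be alleged for severe TEAEs, because TEAEs are also summarised by intensity and the TM BUP summaries may reasonably include that table.

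**Conclusion.** The point holds as a mismatch between a named major safety endpoint and the population in which it is tabulated. Subjects stopped by an AE after TM buprenorphine and before injection belong to the endpoint by definition, and are absent from both parts of its reported proportion. They are missing from the endpoint as tabulated, not from all reporting.

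The size is unknown. In the illustration the understatement is 6.3 to 25.0 percentage points for 1 to 5 such stops. This assumes 15 injected, no post-injection discontinuation, no other early exits, and that an AE ending participation before injection is coded as leading to discontinuation. Neither document states that coding rule.

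A reader might infer that the plan cannot stand without this change. The documents do not support that: the study is descriptive with no hypotheses (SAP 2), this is not one of the key endpoints, and the counts can be recovered from other planned outputs. The grade is should-fix.

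**What to change.** In SAP 5.5.2, add TEAEs leading to study medication discontinuation, and their serious counterpart, to the summaries presented for the TM BUP Analysis Set. Show them for the induction phase, for the period after SUBLOCADE, and overall. Label the overall count, over all subjects given TM buprenorphine, as the result that matches the Protocol 3.3 definition. A footnote should say how an AE that ends participation before injection is coded.

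Keep the Safety Analysis Set table as Protocol 14.3.2 and 14.5 require, and record the addition in SAP 6.2.

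Cost: one or two extra columns in existing AE tables and a few lines of SAP text. No new data are needed. The reported discontinuation rate may look less favourable.
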